1. INTRODUCTION

The Data Safety and Monitoring Board (DSMB) will be responsible for periodic review of the safety data from the NIH/NIDCD-funded study “Non-invasive Brain Stimulation for Swallowing Recovery after a Dysphagic Stroke”. The DSMB will periodically review data on safety. The DSMB will convene according to a planned schedule (refer to Section 6 of this Charter). The DSMB will be responsible for:

- 1) evaluating the incidence all adverse events, particularly those reported with moderate or severe intensity , and all serious adverse events, including death,
- 2) recommending continuing the study or whether a modification or termination of the study is necessary to ensure the safety of all patients,
- 3) monitoring the timeliness and quality of safety data collected during the course of this study.

2. BACKGROUND AND STUDY AIMS

Dysphagia occurs frequently after a stroke and often leads to serious complications. Currently there are no effective therapies for improving swallowing functions in these patients. The usual clinical practice is to supplement nutrition using nasogastric or percutaneous gastrostomy tubes till swallowing improves spontaneously, if at all. These techniques however, do not prevent dysphagia complications like aspiration pneumonia; conversely, they may promote disuse of the swallowing mechanism, increase risk of gastrointestinal bleeding and worsen outcomes in some patients. Implementation of an intervention that improves swallowing in the early aftermath of a stroke can therefore be expected to improve patient outcomes and decrease costs of care.

It has been shown that dysphagia recovery from a hemispheric stroke is associated with an expansion of the swallowing representation in the *unaffected hemisphere*. A treatment approach that facilitates this reorganization in the unaffected hemisphere can help accelerate recovery. Anodal transcranial direct current stimulation (tDCS) is a non-invasive brain stimulation technique that can modulate neuronal excitability of the swallowing motor cortex, and make it more amenable to plastic changes. While it is safe and effective in improving functions in chronic stroke patients, data about its safety and efficacy in acute stroke phase remains sparse. In our pilot study 5 consecutive daily sessions of anodal tDCS to the unaffected swallowing cortex with swallowing exercises was safe and feasible in the acute-subacute stroke phases and showed promise in improving dysphagia. Further confirmation of its safety in early stroke phases and exploration of alternative, more effective doses is vital as a prelude to its examination in confirmatory trials. Besides such **intervention-related factors**, identification of **subject-specific variables** that influence spontaneous swallowing recovery and/or response to the proposed intervention merit examination as they can improve our understanding about the variability of treatment response between subjects, and lead to more efficient study designs by identifying candidates who are more likely to respond to the proposed intervention. We have recently identified a few subject-specific predictors of swallowing recovery from several candidate variables, as outlined in our Preliminary Data. In addition we will use novel neuroimaging measures to obtain surrogate estimates of injury to cortical pathways that regulate

swallowing, and examine the impact of all such subject-related predictors on the effects of our intervention.

Our specific aims are:

Primary Aim: To determine safety and examine effects of 2 different doses of anodal tDCS versus sham stimulation of the swallowing motor cortex of the undamaged hemisphere, combined concomitantly with swallowing exercises, in patients with dysphagia due to an acute-subacute unilateral hemispheric infarction.

Approach:

- A) We will collect data on the effect of our intervention by:
- i) Analyzing changes in penetration and aspiration between the 2 tDCS and sham groups using by a validated assessment tool, the Penetration and Aspiration Scale (PAS) scores;
 - ii) Examining effects of differing doses of anodal tDCS versus sham stimulation on several physiological measures of swallowing, derived from videofluoroscopic swallowing studies;
 - iii) Evaluating durability of any observed effects of tDCS on dietary status as determined by changes in Functional Oral Intake Scale (FOIS) score at study onset and 1 month.
- B) We will assess safety by comparing the anticipated and observed incidence of the following major adverse events in each of the 3 groups: seizures, stroke specific mortality, neurological and swallowing deterioration as measured by changes in NIH Stroke Scale (NIHSS), and FOIS and PAS scores, respectively.

Secondary Aim: To investigate the impact of subject-specific predictors of dysphagia recovery on the outcome of our proposed intervention.

Approach: We will examine differences in the effect size of our intervention across different strata of subject specific-predictors extracted from our pilot model as well as corticobulbar tract (CBT)-lesion load (as a surrogate measure of lesion size and location) by performing a subgroup analysis using regression models.

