3. STUDY DESIGN

3.1.1

Participants

99 stroke patients with dysphagia after an acute/subacute unilateral hemispheric infarction, presenting at Beth Israel Deaconess Medical Center (BIDMC) will be prospectively enrolled, if eligible, into the study. All stroke patients admitted to our hospital receive a standardized dysphagia screening using a bedside water swallow test and are referred for a swallow evaluation to a speech and language pathologist (SLP) if suspected of having dysphagia. Those with moderate to severe dysphagia (PAS ≥ 4) on a standardized videofluoroscopic swallowing (VFSS) evaluation will be invited for participation if they fulfill all study criteria. The patient as well as the SLP will be blinded to the stimulation allocation. Subjects will be randomly assigned to the two intervention or sham groups using PROC PLAN in SAS using a blocking scheme with block size of 6. Subjects will be stratified based on their baseline PAS score (4-6 vs. 7-8) before randomization to the three treatment groups.

3.1.2

Outcomes

Primary Efficacy Outcome: Penetration-Aspiration Score [PAS]: This is a validated 8 point ordinal scale that quantifies penetration and aspiration events observed during VFSS. Since aspiration after stroke is a major predictor of prolonged dysphagia and leads to dietary restrictions, increases the risk of pneumonia and need for tube feeding, this scale will be a relevant measure of swallow status. We have adopted a cut off PAS score ≥ 4 for study enrolment, as minor degrees of penetration can be seen in normal individuals. An average PAS score will be computed based on 5 swallows but if a specific bolus presentation is withheld due to safety concerns, the missing value will be replaced with the worst score (8) for that item.

Primary Safety Outcome: The major safety outcome measures will be **seizures, neurological and motor deterioration or stroke specific mortality** during the period of active stimulation. In light of our small sample size and low expected number of adverse events, we will rely on data from historical cohorts to derive our cut-off numbers for study suspension.

a. Seizures: We expect that a seizure provoked by tDCS would occur during the stimulation session and not thereafter. However, we will analyze the incidence of seizures during the 5 days of active stimulation since excitability changes from tDCS can be prolonged.

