b. Neurological and Motor Deterioration: We will only include neurological deterioration not due to a new stroke, hemorrhagic transformation, or a coexisting encephalopathy. Deterioration will be defined as an increase in the NIHSS by ≥ 4 points between each successive day during active or sham stimulation. NIHSS score will be computed at the bedside by an investigator certified in its performance. Similarly motor deterioration for an individual patient is defined as a ≥ 2 point worsening from baseline on the NIHSS motor sub-item score for a given limb.

c. Swallowing Deterioration: We will record a FOIS score on day 3 of our protocol to assess any deterioration of swallowing with the allocated intervention (tDCS or sham). To minimize

radiation exposure VFSS will not be routinely used for this interim assessment. Subject with ≥ 3 point decrease in FOIS, will undergo an interim VFSS to obtain an interim PAS score. Swallowing deterioration will then be defined as an increase in the PAS score ≥ 2 points compared to baseline score based on this interim assessment not due to other confounding factors outlined above.

d. Stroke specific mortality: Deaths due to direct consequences of brain injury such as brain edema or seizure will count for stroke specific mortality, but not deaths from recurrent ischemic events, hemorrhage, pneumonia, cardiac events, and infections. All deaths will be reported to DSMB who will determine if the death is a possible consequence of tDCS or not.

e. Non serious events such as headaches, skin erythema, fatigue and visual perceptual changes will be tabulated to assess patient tolerability but will not be used as primary safety outcome measures due to their subjective nature. The seriousness of any unexpected adverse events such as a serious skin burn will be promptly reported to the DSMB

Secondary Outcomes: We will use 3 outcomes that assess swallowing physiology, 1 outcome that provides functional (dietary) measure of oral intake, and 3 major safety outcomes.

1. Outcomes of Swallowing Physiology:

a) Pharyngeal Constriction Ratio (PCR): PCR is a measure of the pharyngeal area visible in the lateral radiograph view at the point when a bolus is held in the oral cavity divided by the pharyngeal area at the point of maximum pharyngeal constriction during the swallow.

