Baseline Comparability: While no substantial differences between treatment groups are anticipated given randomization, we will use summary statistics, graphical techniques such as boxplots, and univariate analyses to compare the baseline characteristics of treatment groups. Pre-treatment values will be compared between the placebo- and tDCS-groups using Analysis of CoVariance (ANCOVA) or the Mantel-Haenszel chi-squared test, as appropriate, to determine if the groups are balanced with respect to baseline characteristics while accounting for stratification by dysphagia severity. This comparison will allow us to identify potential confounders to be included in multivariate analyses.

Analytic plan Primary Aim. Primary analysis will use an intent-to-treat approach; thus all randomized subjects will be used in the primary analysis. For the primary outcome variable (PAS) a linear model will be fitted to the data using PROC MIXED in SAS. The outcome will be a change in mean PAS score. Treatment will be included as a categorical variable. Additionally baseline PAS and other variables that will be identified as confounders will be included as covariates. Adjusted means in the two tDCS groups will be compared to those in

the sham group. To control for multiple testing, we will employ the Hochberg-Benjamini procedure, which will result in positive study result if both null hypothesis are rejected at the 0.05 level or one is rejected at the 0.025 level. Similar analyses will be performed on the FOIS, PCR, HLPE, and PDT outcomes. To assess the durability of the intervention effects, a repeated measures analysis will be used. The outcome will be FOIS score at the onset of the trial and at 1 month. Treatment time and their interactions will be included as categorical variables. Additionally other variables that will be identified as confounders will be included as covariates. Adjusted means at the onset of trial and 1 month in the two tDCS groups will be compared to those in the sham group at each time point. *Safety analyses* will be run on all subjects receiving at least one round of intervention. The incidence rates of adverse events will be described as a whole and by treatment group. Adverse events will be presented with and without regard to causality based on the investigator's judgment. *Interim Analyses* No formal efficacy analysis will be performed. The study will not be stopped for early efficacy or futility.

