6.1.1. Evaluation of Safety

The DSMB will review demographic, baseline, treatment exposure, and safety data, including adverse events, serious adverse events, deteriorations and deaths, which will be

summarized prior to each meeting. Data to be reviewed will include tabulations of aggregate data (all data from all patients grouped), tabulations of unblinded comparative outcome data by treatment group, and by-patient listings.

In the role of safety advisory group for this study, the DSMB will:

- 1) evaluate the incidence of deaths, all adverse events, particularly serious adverse events and those reported with moderate or severe intensity, and other relevant measures of patient safety, patient enrollment and study completion status,
- 2) determine whether a modification or termination of the study is necessary to ensure patient safety or recommend continuing the study,
- 3) monitor the conduct of the study, e.g., rate of recruitment, ineligibility, non-compliance with the protocol, dropouts, and balance between treatments with respect to demographics,
- 4) inspect descriptive statistics of average PAS at baseline and Day 5 and of the change from baseline to Day 5,
- 5) inspect descriptive statistics of secondary outcomes (PCR, HLPE, PDT, FOIS, NIHSS) and change from baseline in secondary outcomes at each visit in which they are measured,
- 6) consider whether the trial or dose should be temporarily or permanently stopped based on pre-defined stopping rules for the number of certain type of adverse events. Specifically:
 - a. pause/stop enrollment in a dose if 3/10 or 4/20 in that dose exhibit seizures;
 - b. pause/stop all enrollment if at least 4/20 or 5/40 patients in both active doses combined experience seizure;
 - c. the mortality stopping rule will be the same as the seizure stopping rule; note that the probability for these rules is based on the following assumptions and on the binomial distribution:
 - i. we assume the natural history of the condition yields probability of seizure of 6% and probability of mortality of 7%;
 - ii. probability of stopping the study for safety, if these are the true probabilities, using the above stopping rules, is $\leq 5\%$;
 - iii. thus if a stopping rule is met, odds are that true rates are higher than 6%/7%;

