 - d. a swallowing deterioration for an individual patient is defined as follows: A FOIS change from baseline of ≥ 3 points will trigger a repeat, interim swallowing assessment; swallowing deterioration will then be defined as an increase in the PAS score ≥ 2 points compared to baseline score based on this interim assessment. The stopping rule for a swallowing deterioration is:
 - i. pause/stop enrollment in a dose if 5/10 or 8/20 in that dose exhibit swallowing deterioration;
 - ii. Pause/stop all enrollment if at least 8/20 or 13/40 patients in both active doses combined swallowing deterioration; note that the probability for these rules is based on the following assumptions and on the binomial distribution:
 1. we assume the natural history of the condition yields probability of swallowing deterioration of 20%;

2. probability of stopping the study for safety, if this is the true probability, using the above stopping rules, is $\leq 5\%$;
 3. thus if the stopping rule is met, odds are that true rates are higher than 20%;
- e. a neurological deterioration for an individual patient is defined as a ≥ 4 point worsening from baseline on the NIHSS global impairment score. The same stopping rule for swallowing deterioration will be applied to neurological deterioration.
 - f. A limb deterioration for an individual patient is defined as a ≥ 2 point worsening from baseline on the NIHSS motor score for a given limb. The same stopping rule for swallowing deterioration will be applied to limb deterioration.

These stopping rules will serve as a guideline, not an absolute end-point, for the DSMB to consider stopping the trial.

All reported AEs and AEs considered by the study investigator to be treatment-related (having a relationship of at least possibly study intervention) will be tabulated for all patients who have received any amount of intervention. Tabulations of serious adverse events will be provided. As part of the AE and serious AE tabulations, the incidence of neurological and swallowing deteriorations will be provided. At regularly scheduled meetings the DSMB will be provided with a copy of all SAE Reports. In addition, the DSMB will be notified of any reportable SAEs as soon as possible in between meetings. Any additional information necessary to evaluate the continued safety of all patients enrolled in this trial will also be provided.

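### The safety aim is worded against sham, but the stated method compares each arm with an anticipated rate, and no active-minus-sham estimate of the safety events is planned

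*Combined protocol and SAP*

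**What the plan says.** Section 2 words the Primary Aim as "To determine safety and examine effects of 2 different doses of anodal tDCS versus sham stimulation". Approach B under that aim gives the method: "We will assess safety by comparing the anticipated and observed incidence of the following major adverse events in each of the 3 groups". The events it lists are seizures, stroke-specific mortality, and neurological and swallowing deterioration.

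Section 3.1.2 (Primary Safety Outcome) explains where outside data come in: because the sample is small and few events are expected, "we will rely on data from historical cohorts to derive our cut-off numbers for study suspension". That sentence concerns suspension cut-offs, not the final safety conclusion.

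Section 3.1.6 gives the final safety analysis, in all patients with at least one round of intervention: "The incidence rates of adverse events will be described as a whole and by treatment group". It names no difference, interval or test.

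Section 6.1.1, item 6, holds the only numerical natural-history rates: 6% for seizure, 7% for mortality and 20% for swallowing deterioration. For neurological events, item 6(e) says "The same stopping rule for swallowing deterioration will be applied to neurological deterioration", and item 6(f) does the same for limb deterioration. Neither states a rate of its own.

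**The concern.** The aim and the method do not match. The aim asks how each dose compares with sham. The method asks, separately in each arm, whether the observed rate agrees with an assumed figure. The answer to the second question is only as good as that figure, and a reader cannot check the figures from the text.

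If the assumed rate is above the true background rate in these patients, an active arm with a real excess reads as expected. If it is below, all three arms look worse than expected, and the comparison does not say whether treatment contributed. The randomised sham arm has the same eligibility, exercises, event definitions and observation window, so it measures the background rate directly. The trial is meant to establish safety in early stroke before confirmatory trials, so the basis of its safety conclusion should be the randomised one.

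**Working it through.** **1. Is an active-versus-sham comparison of safety events planned anywhere?**

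- Section 2, Approach B: observed versus anticipated, within each group.
- Section 3.1.6: incidence described overall and by group.
- Section 6.1.1, item 6: stopping counts in the active doses only.
- End of section 6.1.1: the DSMB may weigh differential mortality; no method or threshold.
- Section 6.1.2: each dose versus sham by analysis of covariance, on change scores including NIHSS and FOIS, under the efficacy heading. These are not event incidences.
- Section 10: counts and percentages of seizures, deaths and the three kinds of deterioration.

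None of these is a planned difference in event incidence between an active arm and sham.

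**2. The plan's own figure.** Section 6.1.1 states a stopping probability of at most 5% when the assumed rates are true. With P(X ≥ r), X binomial(n, p):

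- Swallowing, p = 0.20: 5/10 gives 3.3%, 8/20 gives 3.2%, 13/40 gives 4.3%.
- Seizure, p = 0.06: 3/10 gives 1.9%, 4/20 gives 2.9%, 5/40 gives 9.0%.
- Mortality, p = 0.07: 2.8%, 4.7% and 14.5%.

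Taken one at a time, the rules reproduce the figure except 5/40. That mismatch is a separate matter and does not bear on this point.

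**3. Do the anticipated rates fit the events counted?**

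- Window: section 3.1.2 limits the primary safety events to the stimulation period. The 6%, 7% and 20% carry no window.
- Deaths: section 3.1.2 counts only stroke-specific deaths. The 7% is labelled simply as mortality.
- Neurological deterioration: "We will only include neurological deterioration not due to a new stroke, hemorrhagic transformation, or a coexisting encephalopathy". No rate is given for what remains.
- Limb deterioration: no rate; it takes over the rule built on the 20% for swallowing.

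The text does not settle whether the rates are too high, too low or right for these events.

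**4. Illustration by dose.** The counts are assumed: 7/33 in one dose and 1/33 in sham. The 33 per arm is from section 3.1.6 and the 20% from section 6.1.1.

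- Active against 20%: expected 33 × 0.20 = 6.6, observed 7 (21.2%); exact two-sided binomial p = 0.83.
- Active minus sham: 0.2121 − 0.0303 = 0.1818.
- Wilson limits: active 0.1068 to 0.3775; sham 0.0054 to 0.1532.
- Newcombe lower limit: 0.1818 − √[(0.2121 − 0.1068)² + (0.1532 − 0.0303)²] = 0.020.
- Newcombe upper limit: 0.1818 + √[(0.3775 − 0.2121)² + (0.0303 − 0.0054)²] = 0.349.
- Fisher exact p = 0.054.

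With one more sham event (7/33 versus 2/33), the difference is +15.2 points (95% CI −2.0 to 32.3; Fisher p = 0.15).

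**5. How often would the anticipated-rate comparison signal?** The plan names no test, so assume a one-sided 5% exact test against 20% in 33 patients. It needs at least 12 events, since P(X ≥ 11) = 5.1% and P(X ≥ 12) = 2.2%. If the active rate is truly 20%, it signals 2.2% of the time, whatever the sham rate. With an assumed sham rate of 10% or 5%, the expected excess per active arm is 33 × 0.10 = 3.3 or 33 × 0.15 = 4.95 events.

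**6. What could a test against sham show?** Fisher power at 33 versus 33 is 0.7% for 6% versus 2%, 11.5% for 20% versus 10%, and 29% for 20% versus 5%. For 80% power, about 376, 199 and 76 patients per arm would be needed. This argues for an estimate with an interval, not a significance test.

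**The case against.** A reader might infer that the plan sets sham aside in favour of historical data and that an excess would be hidden. The documents do not support that.

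- Sham is one of the three groups in Approach B and goes through the same comparison. In the illustration, 1/33 against 20% gives exact p = 0.009, so the plan's own output would show sham well below the assumed rate.
- Event rates are reported by group in the final analysis (section 3.1.6) and tabulated by group for the DSMB (section 6.1.1). Closed tables carry coded treatments with unblinding on request (section 9). A by-group event table therefore already exists.
- The DSMB may act on differential mortality, and section 6.1.2 compares NIHSS and FOIS change with sham. These scales underlie the deterioration events.
- Historical cohorts are named only for the suspension cut-offs. Approach B says anticipated, and the source of the 20% is not given.
- Pooling the doses makes the example look stronger: 13/66 versus 1/33 gives +16.7 points (95% CI 2.1 to 28.1; Fisher p = 0.031). That rests on an assumed 3% sham rate and fades with one more sham event (13/66 versus 2/33, p = 0.084). By dose, 6/33 and 7/33 versus 1/33 give p = 0.10 and 0.054.
- The text is a DSMB charter that summarises the study, and section 7 lists the clinical study protocol separately. Detail may stand there.

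All of this stands and limits the point. It does not supply the missing piece. Three comparisons with an assumed rate are not an estimate of the difference between arms, change scores are not event incidence, and the mortality provision covers one event without a method. Approach B is also a stated method, so the gap is more than detail left to another document.

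**Conclusion.** The point holds in a limited form. For a safety aim worded against sham, the plan specifies comparison with an anticipated rate inside each group plus descriptive rates, and no active-minus-sham estimate for any safety event. The anticipated rates have no source or window and are absent for neurological and limb deterioration, so agreement with them is weak evidence of safety.

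The size depends on how far the true background rate lies from the assumed one, which the documents do not reveal. In the by-dose illustration, an arm matching 20% almost exactly carries an 18-point excess over sham, with an interval from 2 to 35 points. The counts are assumed, and the documents suggest no particular sham rate. The documents do not show that sham is ignored, that an excess would go unseen, or that the assumed rates are in fact too lenient. This is a cheap improvement to the analysis plan and not a flaw in the design or the randomisation.

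**What to change.** In section 2 (Approach B) and the safety paragraph of section 3.1.6, make the main safety comparison the risk difference versus sham, with a 95% interval suited to small counts (Newcombe, for example). Report it for each dose and for both doses pooled, for each primary safety event. Present it as estimation, without a significance test.

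Keep the anticipated rates as context and for the DSMB boundaries, and add the source, time window and event definition of each. State which anticipated rate applies to neurological and to limb deterioration, and reconcile it with the rule based on 20% that section 6.1.1 applies to them.

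The cost is a few lines of text and one results table; no extra data are needed. The downside is wide intervals with about 33 patients per arm: 2/33 versus 0/33, for example, gives +6.1 points (95% CI −5.2 to 19.6). That width is a fair statement of what the trial can show about rare events.
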